13.1.2 Vaccine efficacy analysis

Primary efficacy analysis will be based on time to infection, which is defined as the time to the first positive blood smear. Arms will be compared by logrank test for interval-censored data (using the interval package in R). VE will be estimated assuming a Weibull model and allowing for interval censoring and stratification by village (survival package in R).

The proportions of infection will be also compared across arms by the exact binomial test, or the Exact Cochran-Mantel-Haenszel test stratifying on village if needed (using the mantelhaen.test in R with the exact option set to true, this is a conditional exact test). Subjects that are censored prior to the last day of planned follow up will be removed from the analysis and censoring will be assumed to be completely at random. A sensitivity analysis may be performed where all censored subjects are treated as either cases or non-cases in either arm.

Under either of these analyses, we will perform an ITT and a per-protocol analysis. Under the per-protocol analysis, subjects that drop out prior to receiving the full number of vaccinations will not be included in the analysis.

The same efficacy analyses will be performed at the end of the main phase and the end of the booster phase.

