13.1.3 Immunogenicity analysis

We will characterize and compare immunogenicity responses between vaccine and placebo arms by Wilcoxon rank sum test or two-sample t-test after proper transformation. We will also compare the immunogenicity response before and after vaccination by Wilcoxon signed rank test or paired t-test after proper transformation. Figures of immune responses in each study arm will be provided to depict the pattern of change in immune responses.

We will explore the impact of PfSPZ Vaccine on the genotype and transcriptome profile of parasites isolated from study subjects using a linear regression or a generalized linear regression.

The same immunogenicity analysis will be carried out at the end of the main phase and the end of the booster phase.

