13.2 Sample Size Consideration

Sample size consideration is primarily based on VE evaluation. Seventy subjects will be enrolled in each arm. If the annual drop-out rate is between 15% and 28%, there will be 50 to 60 available subjects for efficacy evaluation at one year after study initiation. With 50 samples per arm, the study is capable of detecting the protective efficacy of vaccine with 88% power if VE is 45% and the background infection rate is 0.7 (see [Table 8](#)). With 60 samples per arm, the study has 83% power if VE is 45% and background infection rate is 0.6. For safety evaluation, with 70 subjects in each arm, there is 90% probability of observing at least one AE in the arm if the adverse event rate is no less than 0.033.

Based on data from existing studies, the number of participants in the booster phase will be close to that in the main phase. The above sample size consideration should approximately apply to the booster phase.

Table 8: Power for group-wise comparison based on logrank test on time to infection

Sample Size per Arm	Background Infection Rate	Vaccine Efficacy (VE)	Power
50	0.6	0.45	76
50	0.6	0.3	44
50	0.6	0.25	33
50	0.7	0.45	88
50	0.7	0.3	59
50	0.7	0.25	45
60	0.6	0.45	83
60	0.6	0.3	51
60	0.6	0.25	39
60	0.7	0.45	93
60	0.7	0.3	67
60	0.7	0.25	52
70	0.6	0.45	89
70	0.6	0.3	57
70	0.6	0.25	44
70	0.7	0.45	96
70	0.7	0.3	73
70	0.7	0.25	59

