13.3 Randomization and Blinding

Participants in arms 1 and 3a will be enrolled and randomized before the enrollment and randomization of participants in arms 2 and 3b. The study will be randomized with block randomization and stratified by village. To accomplish this, a list of all enrolled subjects will be given to the study statistician at least 2 days prior to the desired time for the first randomization. To prevent dropout before first vaccination, randomization and first administration of vaccination or placebo should occur as close in time as possible.

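### Randomisation is stratified by village, but the efficacy log-rank test has no stated village stratum and the stratified exact test is optional without a criterion; if villages differ in risk, the test is conservative and loses power

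*Combined protocol and SAP*

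**What the plan says.** Section 13.3: "The study will be randomized with block randomization and stratified by village". Arms 1 and 3a are randomised first and arms 2 and 3b later, so there are two separately randomised cohorts, each 70 vaccine to 35 control.

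Section 13.1.2 sets out the efficacy analysis:

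- Endpoint: "Primary efficacy analysis will be based on time to infection, which is defined as the time to the first positive blood smear". This is the primary efficacy analysis, but efficacy is a secondary objective; the trial's primary endpoints are safety (sections 4.1 and 4.2).
- Test: "Arms will be compared by logrank test for interval-censored data (using the interval package in R". No village term is stated.
- Estimate: "VE will be estimated assuming a Weibull model and allowing for interval censoring and stratification by village (survival package in R".
- Proportions: an exact binomial test, "or the Exact Cochran-Mantel-Haenszel test stratifying on village if needed". Nothing says what would make it needed.

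The same methods serve the end of the main phase and the end of the booster phase (13.1.2) and the interim efficacy analysis (13.1.4), in both the ITT and per-protocol sets.

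**The concern.** Blocking within village balances the arms on village. If villages differ in infection risk, that balance makes the difference between arms less variable than under simple randomisation. An unstratified log-rank does not credit this: its variance still includes the between-village variation. It also compares hazards averaged over villages, which pulls the hazard ratio towards 1. The test then rejects too rarely under the null and has less power under the alternative.

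The plan already treats village as relevant to the VE estimate, so leaving it out of the accompanying p-value is an inconsistency. The undefined condition on the stratified exact test leaves the proportion comparison without one fixed method, and this recurs at each analysis. At stake are power in cohorts with only 35 controls each, and a clear link between the p-value and the reported VE.

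**Working it through.** **1. Reproduce the plan's power.** Section 13.2 states: "With 50 samples per arm, the study is capable of detecting the protective efficacy of vaccine with 88% power if VE is 45" per cent and the background infection rate is 0.7. Alpha is not stated; two-sided 0.05 is assumed. VE is read as a reduction in risk, with equal arms and Freedman's formula:

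- vaccine risk = 0.7 × (1 − 0.45) = 0.385
- HR = ln(1 − 0.385) / ln(1 − 0.7) = 0.404
- events = 50 × (0.7 + 0.385) = 54.25
- power = Φ(√54.25 × (1 − 0.404)/(1 + 0.404) − 1.96) = 87.9%, against 88% stated

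All 18 rows of Table 8 reproduce within 0.5 points. So the stated power is that of an unstratified log-rank with equal arms and no village effect.

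**2. Compare the two tests.** With U_k and V_k the log-rank score and variance in village k, the stratified statistic is ΣU_k/√ΣV_k; the unstratified one pools all subjects before forming U and V. Trials were simulated with blocks within village and two-weekly smears, using a log-rank grouped by visit to approximate the interval-censored test. Number of villages and SD of village log hazard are assumptions. For scale, villages at +1 and −1 SD differ in hazard by exp(2 × SD): 1.8-fold at 0.3, 2.7-fold at 0.5, 5.0-fold at 0.8, 7.4-fold at 1.0.

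**3. Within-village HR 0.55, 70:35, five villages.** Power, unstratified to stratified, in three runs (A and B: 1,500 trials per cell, background risk 0.65; C: 600 per cell):

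| SD | A | B | C | Loss (points) |
|---|---|---|---|---|
| 0 | stratifying costs about 1 | 60 to 59 | about 57 to 57 (SD 0–0.3) | about 0 |
| 0.5 | 54 to 57 | 51 to 56 | 55 to 59 | 3–5 |
| 0.8 | 44 to 54 | 46 to 57 | 44 to 59 | 10–15 |
| 1.0 | 41 to 58 | 38 to 56 | 41 to 58 | 17–18 |

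The simulation error of a single power near 50% is about 1.3 points with 1,500 trials and 2.0 with 600. A further run with four villages gave 51.5 to 61.4 at SD 0.6 and 37.7 to 60.3 at SD 0.9, so the size moves with the village assumption.

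**4. Table 8 setting, four villages, 2,500 trials per cell.** Overall risks are held at 0.7 and 0.385. The 50:25 case is 70:35 after 28% drop-out (70 × 0.72 = 50.4; 35 × 0.72 = 25.2). Percentages, unstratified / stratified:

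| SD | Power 50:50 | Power 50:25 | Type I error 50:50 |
|---|---|---|---|
| 0 | 91.4 / 90.8 | 79.0 / 78.0 | 5.2 / 4.8 |
| 0.3 | 91.6 / 92.2 | 78.8 / 80.0 | 4.8 / 5.2 |
| 0.6 | 94.3 / 96.6 | 83.1 / 87.9 | 3.0 / 5.8 |
| 0.9 | 95.6 / 99.2 | 86.9 / 95.3 | 2.0 / 5.5 |

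Power rises with SD because fixing the overall risks lowers the within-village HR, from 0.404 at SD 0 to 0.352 at 0.6 and 0.294 at 0.9. The comparison of interest is within a row: at SD 0.6 the gain is 96.6 − 94.3 = 2.3 points (50:50) and 87.9 − 83.1 = 4.8 points (50:25). With eight villages and SD 0, stratifying costs 92.0 − 90.8 = 1.2 and 78.9 − 77.0 = 1.9 points.

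**5. The Weibull wording.** Write log T = μ + β × arm + σ_k × error. If stratification means a separate σ for each village with shared μ and β, the hazard ratio in village k is exp(−β/σ_k): one VE per village, and no term for the village's level of risk. Large-sample fits (n = 20,000, true VE 45%, SD 0.8) then gave village VEs of 27% to 52% in one set and 25% to 55% in another. Village as a covariate with one σ gave 45% to 46%. The plan does not say which model is meant.

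**The case against.** The strongest reply is that no document says villages differ. Section 6.1 gives one entomological inoculation rate and one prevalence range; the number of villages and village-level rates appear nowhere. The largest losses need about a seven-fold hazard difference between villages at ±1 SD, and the HR 0.55 setting is less favourable than the HR of about 0.40 implied by Table 8. At SD 0 to 0.3 the two tests are equivalent for practical purposes. All of this stands, and it makes the power loss conditional.

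Several stronger inferences are tempting but unsupported:

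- *That significant results would be unsafe.* The error runs the other way: unstratified type I error is about 5% when villages are alike and 2% to 3% at SD 0.6 to 0.9.
- *That the analyst picks the proportion test after seeing outcomes.* The plan does not say when or on what grounds. Village is known at randomisation, so the choice could rest on stratum sizes. The fair criticism is that the criterion is unstated, in a supporting analysis.
- *That stratifying would make the test and the VE interval agree.* An unstratified log-rank and a village-adjusted Weibull test reached different verdicts in 2.0% of 400 trials at SD 0 and 3.5% at SD 0.9 (Table 8 setting, 50:50), a difference within simulation error. Some disagreement comes from pairing a non-parametric test with a parametric estimate and would remain.
- *That the between-arm immunogenicity tests in section 13.1.3 share the defect.* They concern exploratory endpoints, and the section also plans before-after comparisons. Baseline adjustment there is a separate preference.

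Sparse strata are a real limit with 35 controls per cohort, hence the pooling rule below.

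**Conclusion.** The point holds as a conditional loss of efficiency and a gap in specification. The log-rank has no stated village stratum despite village-stratified randomisation, the condition for the stratified exact test is undefined, and the village term in the Weibull model can be read two ways. The loss ranges from nothing to 17 to 18 points across the five-village, HR 0.55 settings, and is about 2 to 5 points in the Table 8 setting at SD 0.6. Those sizes rest on assumed numbers of villages and spreads, two-sided 0.05, and a grouped approximation to the interval-censored test. The Weibull figures also depend on one reading of the text.

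A reader might infer that the plan certainly gives away power; the documents do not support that without village-level risk. Nor is Table 8 wrong on this account. Its use of equal arms when each regimen is compared 70:35 is a separate matter, and matters more unless village differences are large: at SD 0, simulated power is 79.0% at 50:25 against 91.4% at 50:50. The change is still worth making because the exchange is lopsided: a point or two at risk against a possible gain several times larger.

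**What to change.** In section 13.1.2, before unblinding:

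1. State that the main efficacy test is the interval-censored log-rank stratified by village, done separately within cohorts 1/3a and 2/3b. Village scores and variances can be summed as in step 2 of the working.
2. Fix a rule for pooling small villages, based on numbers randomised and not on outcomes.
3. Make the village-stratified exact Cochran-Mantel-Haenszel test the single proportion test, with the same strata, and delete the conditional wording.
4. State that village enters the Weibull model as a covariate with one common shape, so that VE = 1 − HR is one number per regimen.
5. Apply the same specification at each analysis not yet done.

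The cost is a few sentences and a few lines of code, plus about 1 to 2 points of power if villages do not differ. No change to randomisation, visits or data collection is needed.

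### Randomisation is stratified by village, but the log-rank test for efficacy names no village stratum and the proportion test uses village only at discretion

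*Combined protocol and SAP*

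**What the plan says.** Section 13.3 (Randomization and Blinding) states: "The study will be randomized with block randomization and stratified by village". Section 3 adds that each regimen is randomised 2:1 against its own control, and section 4.4 gives 70 vaccine and 35 control subjects per pair.

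Section 13.1.2 (Vaccine efficacy analysis) then treats village in three ways:

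- Time to infection, test: "Arms will be compared by logrank test for interval-censored data (using the interval package in R". No stratum is named.
- Time to infection, estimate: "VE will be estimated assuming a Weibull model and allowing for interval censoring and stratification by village (survival package in R".
- Proportion infected: an exact binomial test or, as the alternative, the "Exact Cochran-Mantel-Haenszel test stratifying on village if needed". Nothing says what would make it needed.

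The same analyses are to be repeated at the end of the main phase and of the booster phase. Section 13.1.4 applies them also to an efficacy interim planned for about December 2018. No section gives a significance level, a decision rule for efficacy, the number of villages, or the variation in infection between villages.

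**The concern.** Blocks within village force the two arms of a pair to be nearly balanced in every village. A difference in transmission between villages can then hardly push the arms apart by chance. An unstratified log-rank test does not use this. Its variance still contains the between-village part, so when villages differ the variance is too large for the way subjects were allocated, and the test rejects too rarely.

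Three things are at stake:

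- Power may be given up in a comparison that has only 35 controls per regimen.
- An unstratified p-value can sit beside a VE interval that allows for village. The two can point different ways, with no rule for which governs.
- The choice between the two proportion tests is open until data are available. Section 7.2 gives the study statistician the allocation list. Under section 13.1.4 the statistician runs the efficacy interim, and the principal investigator, senior investigators and sponsor review it. People who have seen results by arm could therefore make that choice. This last point needs no assumption about village differences.

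**Working it through.** **1. Which test does the stated power belong to?** The table in section 13.2 is titled "Power for group-wise comparison based on logrank test on time to infection". Its inputs are n per arm, background infection rate p_c and VE. Two-sided 5% is assumed, since no level is stated. Freedman's formula with equal arms and no strata is:

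- p_v = p_c(1 - VE); HR = ln(1 - p_v)/ln(1 - p_c); events d = n(p_c + p_v)
- power = Φ(√d × (1 - HR)/(1 + HR) - 1.96)

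For n = 50, p_c = 0.6, VE = 0.45: p_v = 0.33, HR = 0.437, d = 46.5, and power = Φ(6.82 × 0.392 - 1.96) = 76.2% (stated 76). For p_c = 0.7: p_v = 0.385, HR = 0.404, d = 54.25, and power = 87.9% (stated 88). All 18 rows reproduce within 1 point. The formula has no village term, so the table already describes an unstratified test.

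**2. Size and power with and without village strata.** The statistic is Z = (O - E)/√V. At each visit, E = d·n₁/n and V = d(n₁/n)(1 - n₁/n)(n - d)/(n - 1). The unstratified test sums these over visits; the stratified test computes them within village and sums over villages. Allocation is by permuted blocks within village and smears are two-weekly. Village log-hazards are normal with the SD shown. Village numbers and SDs are assumptions.

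Simulation A: overall infection held at 0.60 versus 0.33 (VE 45%), 12 visits, 3, 6 or 12 equal villages, arms 50:50 and 70:35, 3,000 runs per cell. Ranges run over these six layouts.

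| SD | Size, unstratified | Size, stratified | Power, unstratified | Power, stratified | Change in power, points |
|---|---|---|---|---|---|
| 0 | 4.6-5.6% | 4.4-5.5% | 78.1-79.6% | 75.4-79.4% | -2.7 to 0 |
| 0.4 | 3.7-4.4% | 4.5-5.6% | 80.1-81.1% | 80.0-82.6% | -0.9 to +1.7 |
| 0.8 | 2.3-3.8% | 4.8-5.9% | 82.5-84.2% | 88.2-90.2% | +5.5 to +6.2 |
| 1.2 | 1.4-2.5% | 5.0-5.6% | 84.0-86.3% | 93.2-95.8% | +9.0 to +10.6 |

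Simulation B: 70:35, blocks of 3, control infection 0.65 at the median village, within-village HR 0.5, 10% dropout, 13 visits, 4,000 runs per cell. The layouts are one village of 45 plus five of 12, and one of 15 plus nine of 10. The 10% lies within the plan's annual 15 to 28% taken over half a year (1 - √0.85 = 7.8%; 1 - √0.72 = 15.1%).

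| SD | Size, unstratified | Size, stratified | Power, unstratified | Power, stratified | Change in power, points |
|---|---|---|---|---|---|
| 0 | 4.9-5.7% | 5.1% | 67.0-67.3% | 64.7-66.0% | -2.6 to -1.0 |
| 0.3 | 4.2-4.3% | 4.9-5.0% | 66.4-67.0% | 65.2-67.0% | -1.2 to 0 |
| 0.5 | 3.5-4.3% | 4.8-5.8% | 62.6-63.3% | 64.4-67.0% | +1.8 to +3.7 |
| 0.8 | 3.2-3.3% | 5.3-5.6% | 55.0-55.6% | 64.6-65.0% | +9.4 to +9.6 |
| 1.0 | 2.0-2.4% | 5.1-5.6% | 47.8-48.8% | 64.1-64.3% | +15.5 to +16.3 |

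The Monte Carlo standard error of a 5% size is √(0.05 × 0.95/3000) = 0.4 points in A and 0.3 points in B. The gains differ at SD 0.8 because A holds the overall infection rates fixed, whereas B fixes the within-village effect, so its overall effect shrinks as SD rises.

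**3. What the SDs mean.** The 95% range of village hazards spans a factor exp(2 × 1.96 × SD): about 5-fold at SD 0.4, 7-fold at 0.5, 23-fold at 0.8, 50-fold at 1.0 and 110-fold at 1.2.

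**The case against.** The strongest reply is that the harm is conditional. The sites are one community and its surrounding villages, and nothing in the documents supports a 23-fold spread in hazard. At smaller spreads the gain is a few points or nothing, and with many small villages stratifying costs power. This stands, and it limits the claim.

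A reader might go further and infer any of four things that the documents do not support:

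- *That the test is conservative and loses power as a matter of fact.* Both depend on a village effect that is not quantified.
- *That this is the p-value that decides the trial.* Efficacy is a secondary endpoint (section 4.2) in a Phase 1 study with a safety primary endpoint, and no level or decision rule is given. It is the only test named for the primary efficacy analysis, and the sample size rests on it, but no more than that.
- *That the stated power is therefore too high.* The table reproduces with an unstratified formula, so this omission does not inflate it.
- *That false positives are at risk.* The unstratified log-rank test errs towards caution.

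Limits of the check also stand. The simulations used a grouped log-rank test at common visits, not an interval-censored permutation test. The stratified test ran slightly above 5% in some cells, so a little of its gain may come from that. The exact proportion tests were not simulated. How often the p-value and the VE interval would disagree was not estimated, and some disagreement could remain after the fix because a log-rank test and a Weibull interval are different procedures.

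What the reply does not remove is the mismatch between design and analysis, or the undefined trigger for the proportion test.

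**Conclusion.** The concern holds in a conditional form. The plan randomises within village, names no village stratum for the log-rank test, allows for village in the VE estimate, and leaves it discretionary in the proportion test. No other section reconciles these.

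If villages differ in infection risk, the unstratified test is conservative and can lose power. Under the assumed village layouts, size falls to about 4% at SD 0.4 to 0.5, where stratifying moves power by -1 to +4 points. At SD 0.8 size is about 2 to 4% and stratifying gains 5 to 10 points. Larger gains appear only at SDs of 1.0 and above, which imply at least a 50-fold spread. With little or no village effect, stratifying gains nothing and may cost up to about 3 points.

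This is a cheap improvement, not a flaw that invalidates the analysis.

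**What to change.** In section 13.1.2:

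- State that each regimen is compared with its own control by an interval-censored log-rank test stratified by village, with scores computed or permuted within village.
- Delete 'if needed', so that the exact Cochran-Mantel-Haenszel test on village is the proportion test.
- Pool small villages by a rule fixed in advance on village size alone, without reference to arm or outcome. The statistician holds the allocation list, so a rule that looks at which arms a village contains would reopen the discretion.
- Use the same strata for the VE estimate.

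An efficacy interim was planned for about December 2018. For any analysis already run or reviewed unblinded, report the stratified test as a dated change, alongside the unstratified test now in the plan. Apply it prospectively to the booster phase.

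The cost is SAP wording and a few lines of code, with no new data, and up to about 3 points of power if villages hardly differ.

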Data represents total # of individual subjects experiencing AE (% of subjects experiencing AE).
Each vaccine receipt is counted once at worst severity for any laboratory abnormality.
There were no severe laboratory abnormalities.

P. falciparum infections as recorded starting 28 days post vaccination 5 occurred significantly earlier in the control group than the PfSPZ Vaccine group; interval censored log-rank $p=0.01$ (VE based on Cox HR, 48.27% 95% CI (14.45, 68.72)). The proportion of individuals with any infection as recorded starting 28 days post vaccination 5, during the malaria season, was 28.8% lower (95% CI 8.2-47.2, $p=0.006$) in the PfSPZ Vaccine group than the control group. The non-parametric maximum likelihood estimation (MLE) curves, accounting for interval censoring, for the vaccine and placebo groups in the Mali trial are presented in [Figure 1](#) (Sissoko et al., 2017).

[figure not shown]
Figure 1: Protective Efficacy: First Positive Blood Smear (BS) Starting 28 Days Post Vaccination #5

In the pilot safety group 7/9 (78%) were blood smear (BS) positive. Protective efficacy was analyzed by time to first positive BS, with Day 0 at 28 days after the fifth vaccination. The inverse survival curves include participants who received all five vaccinations and were evaluable for the primary exploratory efficacy endpoint. Five subjects (1 PfSPZ Vaccine; 4 placebo) were censored from primary efficacy analysis as they had a positive BS prior to 28 days post Vaccination #5.

PfSPZ vaccination induced only modest antibody responses to CSP and antibody levels. Antibody levels were not significantly predictive of infection in the vaccine arm subjects. When results of the *Plasmodium falciparum* circumsporozoite protein (PfCSP) enzyme-linked immunosorbent assay (ELISA) were compared between the USA volunteers and the Tanzanian and Malian volunteers, it was clear that antibody responses to PfSPZ Vaccine were lower in malaria-exposed than in malaria-naive subjects. **Figure 2** shows the PfCSP ELISA results (net OD 1.0) after three doses for volunteers in VRC 314 and WRAIR 2080 (N = 36) who received four or five doses of 2.7×10^5 PfSPZ/dose versus volunteers in 14-I-N010 (N = 41) who received five doses of 2.7×10^5 PfSPZ/dose.

Figure 2: USA vs Mali PfCSP ELISA Results

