1.7 Rationale for administering the booster dose (4th vaccination)

The main phase of the study was designed to assess the safety and immunogenicity of two different vaccine regimens, an established regimen of 0, 8 and 16 weeks and a condensed regimen of 0, 1, and 4 weeks. The study started in June 2018 and the 3rd vaccination in all *Arms* was administered in September 2018. Currently, the participants are nearing the end of the malaria follow up phase during the first transmission season. The current plan is to extend the study by evaluating the safety and immunogenicity in the second transmission season after administration of a booster vaccination.

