6.1 Clinical Site

The study will be carried out in collaboration between the Laboratory of Malaria Immunology and Vaccinology (LMIV) (National Institute of Allergy and Infectious Diseases [NIAID], National Institutes of Health [NIH]), the Malaria Research and Training Center (MRTC) in Bamako, Mali, and Sanaria, Inc. MRTC is experienced in conducting Good Clinical Practice (GCP) compliant clinical trials including two malaria vaccine and drug studies.

The study will be carried out in Ouelessebougou and surrounding villages, a community located 80 km south of Bamako. Ouelessebougou village has been conducting ongoing clinical research since 2006 and is endemic for malaria with marked seasonality and a high burden of malaria in both children and adult populations.

For the purpose of vaccine trials, adequate facilities for conducting an interventional trial have been put in place at Ouelessebougou within walking distance to the residents' homes. The

study site has a research clinic with an inpatient unit. Study physicians are available 24 hours a day, seven days a week.

At Ouelessebougou, the malaria transmission is highly seasonal, with the transmission season taking place from June until December, with peak transmission in August to November. Ouelessebougou is situated in a high transmission area, with entomological inoculation rates using CDC light traps of about seven infectious bites per person over the period of August to December (Dicko et al., 2011). Malaria parasite prevalence during the transmission season varies between 20-30% in adults (unpublished data).

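### VE is estimated from a Weibull model with a monotone hazard in a highly seasonal setting; under plausible seasonal shapes its nominal 95% CI covers about 91-94% and VE reads about 1-3 points high

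*Combined protocol and SAP*

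**What the plan says.** On testing, protocol section 13.1.2 states: "Arms will be compared by logrank test for interval-censored data (using the interval package in R"). On estimation it states: "VE will be estimated assuming a Weibull model", with interval censoring handled and the fit stratified by village, using R's survival package. It names no method for the VE confidence interval and plans no flexible baseline, robust variance, fit check or semiparametric sensitivity estimate. The same efficacy analyses serve the main and booster phases, and section 13.1.4 applies them to the interim analysis meant to help choose a regimen for later studies.

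Section 6.1 calls transmission highly seasonal, "with the transmission season taking place from June until December, with peak transmission in August to November". Section 1.7 says the third dose in all arms "was administered in September 2018". Section 3.1 has artemether/lumefantrine given before doses 3 and 4, and about six months of follow-up after each. On village, section 13.3 says: "The study will be randomized with block randomization and stratified by village".

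**The concern.** The Weibull hazard is h(t) = λk·t^(k-1): it rises throughout if k > 1, falls throughout if k < 1, and is flat if k = 1. The calendar suggests something else. The booster is given before the peak and follow-up ends after it. The main phase starts inside the peak and continues after transmission has largely stopped, possibly with a low-risk period just after antimalarial treatment. If the fitted shape is wrong, the model-based standard error need not be valid and VE can be displaced even when hazards are truly proportional.

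VE and its interval are what readers will take from the efficacy analysis. The first Mali trial is reported as "VE based on Cox HR" (section 1.4.3.1), which makes no assumption about the baseline. There is also an ambiguity over village. In the survival package's parametric regression, a strata term gives each village its own scale, and one coefficient then implies a different VE in each village.

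**Working it through.** **1. The plan's own figure.** Table 8 gives 88% logrank power for 50 per arm, background 0.7 and VE 45%. Taking VE as 1 minus the ratio of infection proportions, the vaccine-arm proportion is 0.7 × 0.55 = 0.385 and HR = ln(0.615)/ln(0.30) = 0.404. Freedman's formula with 50 × (0.7 + 0.385) = 54.25 events gives √54.25 × (1 - 0.404)/(1 + 0.404) - 1.96 = 1.17, or 87.9% power. Two-sided 0.05 is assumed because none is stated. All 18 rows agree within 2 points. This power is for the logrank test and does not depend on the Weibull model. Section 13.1.2 does not define VE for the Weibull fit; below, VE = 1 - HR.

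**2. Inputs.** Allocation is 2:1 (section 3). The sizes are 70:35, or 60:30 after the lower dropout rate in section 13.2. Smears are every 14 days (section 1.7.2), with a last visit at day 182 (Appendix A). Background 0.7 and VE 45% are from section 13.2. The main phase starts in mid-September. The booster starts about 8 June (38 weeks later, section 3.1) or mid-July (about 10 months later, section 3). The hazard shapes are assumptions, because the protocol gives only calendar months.

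**3. Large-sample check.** For VE 30-45% and background 0.6-0.7, the fitted Weibull VE was 0.0 points off under constant and true-Weibull hazards, with a model SE 1.00 times the sandwich SE. Under seasonal shapes it was 0.4 to 2.9 points too high, with a model SE 0.89-0.98 of the sandwich SE. The two plateau-type booster shapes gave only 0.4 to 1.1 points.

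**4. Simulation.** 60:30, true VE 45%, background 0.7, 1500 trials per row. The comparator is a complementary log-log proportional-hazards model with one free intercept per visit interval.

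| Assumed hazard | Mean Weibull VE minus free-baseline VE (points) | Weibull SE ÷ SD | Coverage, Weibull | Coverage, free | SD of log HR, Weibull / free |
|---|---|---|---|---|---|
| Constant (control) | 0.0 | 1.04 | 95.8% | 95.8% | 0.279 / 0.279 |
| True Weibull, k = 1.5 (control) | 0.0 | 0.97 | 94.7% | 94.8% | 0.298 / 0.299 |
| Main: flat to end November, falls in December, then near 0 | 1.6 | 0.94 | 93.4% | 94.7% | 0.309 / 0.292 |
| Main: same, 21-day initial lag | 2.7 | 0.89 | 90.8% | 95.0% | 0.325 / 0.291 |
| Main: flat to day 45, gradual fall to day 105 | 1.5 | 0.90 | 91.6% | 94.5% | 0.323 / 0.302 |
| Booster, 8 June: rise to August, plateau to end | 0.6 | 0.94 | 93.1% | 93.5% | 0.309 / 0.302 |
| Booster, mid-July: rise, plateau to end November, fall | 1.0 | 0.92 | 93.5% | 94.4% | 0.316 / 0.304 |
| Booster, mid-July: peak September-October | 1.6 | 0.92 | 92.6% | 94.9% | 0.314 / 0.295 |
| Booster: bell at day 80, SD 40 days | 1.5 | 0.94 | 93.4% | 95.0% | 0.308 / 0.292 |
| Booster: bell at day 80, SD 25 days | 2.5 | 0.89 | 91.8% | 95.1% | 0.328 / 0.295 |

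Monte Carlo error on coverage is √(0.95 × 0.05/1500) = 0.6 points. At 70:35 the seasonal rows gave 0.7 to 2.9 points and Weibull coverage of 91.9-93.9%. A sandwich SE brought Weibull coverage to 93.7-95.8% over both sample sizes but does not remove the shift.

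**5. Consistency.** An SE that is 0.89 of the true SD gives coverage 2Φ(1.96 × 0.89) - 1 = 91.9%; at 0.97 it gives 94.3%. The narrow SE therefore explains most of the shortfall.

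**6. Village scales.** With strata-specific scales, VE in village v is 1 - exp(-β/scale_v), where β is the log-time coefficient. For illustration only, β = 0.477 gives 1 - exp(-0.477/0.65) = 52% at scale 0.65 and 1 - exp(-0.477/1.2) = 33% at scale 1.2.

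**The case against.** The strongest objection is that the decision rule is sound. The arms are compared by a nonparametric logrank test and, separately, by exact tests of proportions; no Weibull test is planned. At VE = 0 the Weibull interval excluded zero in about 6-9% of simulated trials (coverage 91-94%). A reader might infer that the trial's false-positive rate is inflated to that level. The documents do not support that inference, because the planned p-value does not come from this model. The figure describes only how often the interval would wrongly exclude zero.

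Second, the undercoverage is conditional. The plan names no interval method, and the shapes are assumed. The main phase starts inside the peak, so its hazard mostly falls, which a Weibull allows. The misfit there comes from the sharp end of season and from any lag after treatment, whose length the documents do not give. This stands, and it is why the result is a range.

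Third, the shift is small. With an SD of log HR near 0.3, the 95% interval around VE 45% is 1 - exp(ln 0.55 ± 0.588), or about 1% to 69%. Three points of VE is ln(0.52/0.55) = -0.056, about a fifth of that SD. Some of the Weibull excess over the truth is small-sample behaviour, since the free-baseline median itself missed by up to 1.6 points. For that reason the table shows differences on the same data.

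Fourth, efficacy is a secondary objective of a Phase 1 trial. Comparability also argues only partly for change: section 1.4.3.3.2 does not name the VE model of the second Mali trial.

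Finally, a reader might infer that village VEs of 52% and 33% are to be expected. Those scales are invented, and section 13.1.2 does not say that strata-specific scales will be fitted. Only the need to clarify the wording stands.

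**Conclusion.** The point holds as a moderate one about estimation. Under main-phase and peaked booster shapes consistent with section 6.1, and with the default model-based SE, the nominal 95% interval covers about 91-94% and VE is about 1-3 points high. A separate simulation of 800 replicates, also at 60:30 and background 0.7, gave 91-94% for the Weibull against 93-96% for the free baseline on those shapes.

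The effect is not uniform. For a booster season that rises to a plateau, the shift is about 1 point or less. Weibull coverage there was 93.1-93.7% in the 1500-trial runs and 94-95% in the 800-replicate run, close to the free baseline. In the other direction, one further set of assumed main-phase shapes gave 89.2% coverage, and background 0.8 or a very narrow peak gave shifts of 3.4 to 4.1 points. No calculation was made for the shorter interim follow-up.

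The logrank test and Table 8 are unaffected. The practical consequence is a reported interval that is somewhat too narrow and can disagree with the planned test.

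**What to change.** Make the main VE estimate 1 - HR from an interval-censored proportional-hazards model with an unspecified baseline, with village as a covariate and one common HR. Prefer a fit that uses each subject's own smear interval, since follow-up visits have windows of up to ±5 days (Appendix A) and unscheduled positive smears occur (section 8.5). A complementary log-log model by visit interval is a simpler alternative. State the interval method. Keep the Weibull fit, with a robust SE, as a sensitivity analysis.

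Do not fit a separate free baseline per village. The documents do not give the number of villages. With six assumed, that estimator gave median VE 47.9-48.3% for a true 45% and coverage 92.7-93.0%, no better than the Weibull; with three it was acceptable. If the Weibull model is kept with village adjustment, state that a single common scale is used.

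The cost is SAP wording, a little more analysis work and a baseline with more parameters. When the Weibull model was true, the SD of log HR was 0.299 against 0.298, so essentially no precision is lost.
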